- Describe the prevalence of pre-specified birth outcomes other than major congenital malformations according to exposure (yes/no) to pregabalin any time during pregnancy, and after exposure to lamotrigine, exposure to duloxetine, and exposure to lamotrigine or duloxetine any time during pregnancy;
 - Estimate the association between in utero exposure to pregabalin any time during pregnancy and the birth outcomes other than major congenital malformations, as compared with no exposure to pregabalin; exposure to lamotrigine; exposure to duloxetine; and exposure to lamotrigine or duloxetine.

The secondary objectives of the study are to:

- Estimate the incidence rates of pre-specified postnatal neurodevelopmental outcomes according to exposure (yes/no) to pregabalin any time during pregnancy, and after exposure to lamotrigine, exposure to duloxetine, and exposure to lamotrigine or duloxetine any time during pregnancy;
- Estimate the association between in utero exposure to pregabalin any time during pregnancy and the pre-specified postnatal neurodevelopmental outcomes, as compared with no exposure to pregabalin; exposure to lamotrigine; exposure to duloxetine; and exposure to lamotrigine or duloxetine.

Study design: This PASS is a population-based cohort study using administrative registries from four Nordic countries: Denmark, Finland, Norway, and Sweden.

Population: The study population consists of all pregnancies identified in the respective administrative registries from 1 January 2005 to 31 December 2015 in Denmark, Finland, and Norway and all pregnancies identified from 1 July 2006 to 31 December 2013 in Sweden.

Variables:

Exposure to medications under study is defined as follows:

Pregabalin exposure- At least one dispensing of pregabalin during pregnancy in the first trimester for the outcome of major congenital malformation and during any trimester for all remaining outcomes.

Comparator/reference groups:

Unexposed- This reference group consists of women who had no dispensing for pregabalin or other antiepileptic drugs (AEDs) including lamotrigine, and no dispensing for duloxetine during the first trimester for the outcome of major congenital malformations and during any trimester for all remaining outcomes.

Lamotrigine exposure- At least one dispensing of lamotrigine during the first trimester for the outcome of major congenital malformations and during any trimester for all remaining outcomes.

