6. RATIONALE AND BACKGROUND

Pregabalin (Lyrica[®], Pfizer Inc., New York, NY) was approved in July 2004 by the European Medicines Agency (EMA) for the treatment of peripheral neuropathic pain and as an adjunctive therapy for adult patients with partial onset seizures. Subsequently, the marketing authorizations were expanded to include generalized anxiety disorder (GAD), in March 2006 and central neuropathic pain, in September 2006. Per current European Union (EU) label, “Lyrica[®] should not be used during pregnancy unless clearly necessary (if the benefit to the mother clearly outweighs the potential risk to the foetus).”¹ In the general population (including men and women of all ages), pregabalin is mostly used for neuropathic pain (18-98%) and least used for epilepsy (4-6%).² Use of pregabalin in non-pregnant population, as assessed in a study in Sweden, is primarily for neuropathic pain (36%) and only 1.3% for epilepsy, with 40% of pregabalin initiators having no identifiable approved indication based on routine records.³ Published data on the most common indication in pregnant women are unavailable at this time. A study based on two distinct United States (US) datasets reported an epilepsy indication frequency of 5.5% and 6.7% of pregabalin use in pregnant women.⁴ In the feasibility assessment for this study, based on available Danish data, 21% of pregnancies exposed to pregabalin in the first trimester had a known indication identifiable by a hospital diagnosis in the previous year. Those included epilepsy (4% of those with identifiable indication), neuropathic pain (72% of those with identifiable indication), or GAD (24% of those with identifiable indication). Frequency distributions were similar for pregnancies exposed to pregabalin at any trimester (Table 1).

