- during gestation, according to exposure to lamotrigine any time during gestation, according to any in utero exposure to duloxetine, according to any in utero exposure to lamotrigine or duloxetine, and in live or stillborn children unexposed in utero to antiepileptics;
- Estimate the association between any in utero exposure to pregabalin and the birth outcomes other than major congenital malformations, as compared with no exposure to pregabalin; any in utero exposure to lamotrigine; any in utero exposure to duloxetine; any in utero exposure to lamotrigine or duloxetine, and no in utero exposure to antiepileptics.
 - Estimate, in a sensitivity analysis to evaluate potential impact of selection bias, association between first-trimester exposure to pregabalin and prevalence of major congenital malformations, as compared with no first-trimester exposure to pregabalin; first-trimester exposure to lamotrigine; first-trimester exposure to duloxetine; and first-trimester exposure to lamotrigine or duloxetine, in pregnancies ending in livebirth, stillbirth, or 2nd trimester induced abortion (in Denmark, Finland and Norway);

The specific secondary objectives of the study are to:

- Describe, in liveborn infants, the incidence rates (number of incident outcome events/postnatal person time) of pre-specified postnatal neurodevelopmental outcomes (listed in [Section 8.3.2.2](#)) according to exposure (yes/no) to pregabalin any time during pregnancy, after any in utero exposure to lamotrigine, after any in utero exposure to duloxetine, and after any in utero exposure to lamotrigine or duloxetine in pregnancies ending in live birth;
- Estimate, in liveborn infants, the association between in utero exposure to pregabalin and the pre-specified postnatal neurodevelopmental outcomes, as compared with no in utero exposure to pregabalin; any in utero exposure to lamotrigine any in utero exposure to duloxetine, and any in utero exposure to pregabalin or duloxetine.

The calculations of ‘prevalence’ and ‘incidence rate’ are further described in section 8.7.1 and section 8.7.2 respectively.

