8.3. Variables

8.3.1. Exposures

For the purposes of timing of exposure, trimesters of pregnancy will be defined as follows:

- First trimester: from the first day of the last menstrual period (LMP)-90 days to LMP+97 days (both dates inclusive);
- Second trimester: from LMP+98 days to LMP+202 days (both dates inclusive);
- Third trimester: from LMP+203 days (inclusive) until pregnancy end date (not included).

Exposure during the first trimester

Pregabalin exposure during the first trimester will be defined as at least one maternal dispensing of pregabalin during the first trimester. Pregabalin monotherapy in the first trimester will be defined as first-trimester exposure to pregabalin and no first-trimester dispensing for any other AED.

Comparators:

Unexposed to pregabalin during the first trimester comparator is defined as pregnancies without a dispensing for pregabalin or any other AED, including lamotrigine or duloxetine, during the first trimester.

Lamotrigine exposure in the first trimester is defined by at least one dispensing of lamotrigine during the first trimester. Lamotrigine monotherapy in the first trimester will be defined as first-trimester exposure to lamotrigine and no first-trimester dispensing for any other AED.

Duloxetine exposure in the first trimester is defined by at least one dispensing of duloxetine during the first trimester. Duloxetine monotherapy in the first trimester will be defined as first-trimester exposure to duloxetine and no first-trimester dispensing for any AED.

Lamotrigine or duloxetine exposure in the first trimester is defined by at least one dispensing of lamotrigine or duloxetine or both during the first trimester. Lamotrigine or duloxetine monotherapy in the first trimester will be defined as first-trimester dispensing of lamotrigine or duloxetine or both and no first-trimester dispensing for any other AED.

For analyses that use lamotrigine as the comparator, pregnancies exposed to both pregabalin and lamotrigine in the first trimester will be excluded. For analyses that use duloxetine as the comparator, pregnancies exposed to both pregabalin and duloxetine in the first trimester will be excluded.

Exposure any time during pregnancy

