Pregabalin exposure any time during pregnancy is defined by at least one dispensing of pregabalin during any trimester. Pregabalin monotherapy any time during pregnancy will be defined as any-pregnancy exposure to pregabalin and no dispensing for any other AED during any trimester.

Comparators:

Unexposed to pregabalin during any trimester comparator is defined as pregnancies without dispensing for pregabalin or other AEDs including lamotrigine, or duloxetine during any trimester.

Lamotrigine exposure any time during pregnancy is defined by at least one dispensing of lamotrigine during any trimester. Lamotrigine monotherapy any time during pregnancy will be defined as any-pregnancy exposure to lamotrigine and no dispensing for any other AED during any trimester.

Duloxetine exposure any time during pregnancy is defined by at least one dispensing of duloxetine during any trimester. Duloxetine monotherapy any time during pregnancy will be defined as any-pregnancy exposure to duloxetine and no dispensing for any AED during any trimester.

Lamotrigine or duloxetine exposure any time during pregnancy defined by at least one dispensing of lamotrigine or duloxetine or both during any trimester. Lamotrigine or duloxetine monotherapy any time during pregnancy will be defined as any-pregnancy exposure to lamotrigine or duloxetine or both and no dispensing for any other AED during any trimester.

For analyses that use lamotrigine as the comparator pregnancies exposed to both pregabalin and lamotrigine in any trimester will be excluded. For analyses that use duloxetine as the comparator pregnancies exposed to both pregabalin and duloxetine in any trimester will be excluded.

In a sensitivity analysis, monotherapy with pregabalin, lamotrigine, and/or duloxetine will be defined by absence of other AED, selective serotonin reuptake inhibitors, or benzodiazepines.

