8.4. Data sources

Data sources used to construct the analysis data set for this study are presented in Table 3. Within each country, records from all registries are linkable at the individual level by a unique national person identifier. For births recorded in the birth registries, a maternal unique identifier is a variable on the record of the offspring, enabling exact linkage between a given offspring and maternal history of medication dispensing or diagnoses before or during pregnancy.

Diagnosis in all countries are registered based on the ICD-10 coding system and accessed through registers as specified in Table 3. Similarly medications are classified according to the ATC coding system and accessed through prescription registers. The medical birth registers in the included countries furthermore contain similar information other relevant covariates (calendar year of delivery, maternal age at conception, parity; marital/cohabiting status; pregravid body mass index (BMI); smoking during pregnancy; single or multiple pregnancy; and child's sex.)

Validity of routine data in Nordic national registries has been found to be high in all countries.²²⁻³⁷ In Denmark, positive predictive value of diagnoses of cardiac malformations is 89%.³⁸ For drugs used chronically, there is also high level of agreement between general practitioner and dispensing records.³⁹ An agreement between dispensing records and drug use reported in the standard medical antenatal records included in the birth register was 69% for antiepileptics in Sweden.⁴⁰

Table 3. National registries in Denmark, Finland, Norway and Sweden and type of data available from each registry

Study variable/role	Type of data	Data source(s)	Coding system(s) used
Person identification (mothers and children)	Unique personal identifier for data linkage	Danish Civil Registration System ⁴¹ Danish Civil Registration System Finnish Medical Birth Register* National Registry of Norway Swedish Total Population Register ⁴²	N/A
Study population	Pregnancies ending in singleton/multiple live birth or stillbirth	Danish Medical Birth Registry Finnish Medical Birth Register* Medical Birth Registry of Norway Swedish Medical Birth Register Danish National Patient Registry ^{43,44}	A specific variable in each birth registry

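### Exposure is counted from 90 days before LMP although the objectives concern in-utero exposure, and no planned analysis tests what this does to the comparison with unexposed pregnancies

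*Protocol*

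**What the plan says.** Section 8.3.1 defines the window: "First trimester: from the first day of the last menstrual period (LMP)-90 days to LMP+97 days (both dates inclusive". The rule for malformations is "Pregabalin exposure during the first trimester will be defined as at least one maternal dispensing of pregabalin during the first trimester". For all other outcomes, "Pregabalin exposure any time during pregnancy is defined by at least one dispensing of pregabalin during any trimester", so the earliest qualifying date is again LMP-90. Lamotrigine follows the same rule ("Lamotrigine exposure in the first trimester is defined by at least one dispensing of lamotrigine during the first trimester"), as does duloxetine, and the unexposed group must be free of these drugs and of other antiepileptics over the same window.

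The target is worded differently. The Abstract has "At least one dispensing of pregabalin during pregnancy in the first trimester for the outcome of major congenital malformation", and section 7 has "Estimate the association between any in utero exposure to pregabalin and the birth outcomes other than major congenital malformations". Section 7 also describes malformation prevalence after exposure in utero.

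Section 8.7.6 lists two kinds of sensitivity analysis: adding second-trimester terminations, and a stricter definition of monotherapy. Neither changes the exposure window. Section 8.9 concedes that dispensing records may misstate how much drug was taken and when. It does not mention the 90 days before LMP or the likely direction of bias.

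**The concern.** No rule in the protocol requires a dispensing on or after LMP, or supply that reaches past it. A woman who filled one prescription at LMP-90 and stopped before conceiving contributes an exposed pregnancy to the malformation analysis, and also to the analyses of Apgar score, growth and neurodevelopment. That some women stop is plausible, because section 6 cites the label text that the drug "should not be used during pregnancy unless clearly necessary". How many stop, and when, is not in the protocol.

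Section 6 calls exposed versus unexposed the primary comparison. In that comparison, unexposed fetuses in the exposed group would be expected to weaken a real excess risk. That is the reassuring direction, in a safety study prompted by a reported three-fold increase. An upper confidence limit from such a group would then be read as a statement about in-utero exposure that it does not fully support.

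**Working it through.** **Window.** LMP-90 to LMP+97, both days included, is 90 + 1 + 97 = 188 days. Of these, 90 (48%) precede LMP. This is a share of days, not of exposed pregnancies.

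**Reproducing the plan's figure.** Inputs from section 8.5 and Table 5: 1000 exposed, 119 comparators per exposed, prevalence 3%, true ratio 1.0, two-sided 95% interval, 80% probability.

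- Expected cases: 1000 × 0.03 = 30 exposed; 119,000 × 0.03 = 3570 comparator.
- SE of log ratio = √(0.97/30 + 0.97/3570) = 0.1806.
- Limit = exp[(1.960 + 0.842) × 0.1806] = 1.658, against the stated 1.65845.

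The stated figure is correct for exposure as section 8.3.1 defines it.

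**Translation to in-utero exposure, against unexposed.** Let s be the share of the classified-exposed group with no in-utero exposure. With confounding controlled, observed ratio = 1 + (1 − s)(true ratio − 1). An observed limit of 1.658 therefore corresponds to a true ratio of 1 + 0.658/(1 − s). The protocol does not give s, so 10% to 50% is an assumed range. The last column applies the first formula for the limit to 1000 × (1 − s) exposed, with the ratio still 119:1.

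| s | True ratio matching 1.658 | True 2 is observed as | True 3 is observed as | Limit if only the 1000 × (1 − s) truly exposed are kept |
|---|---|---|---|---|
| 10% | 1.73 | 1.9 | 2.8 | 1.70 |
| 20% | 1.82 | 1.8 | 2.6 | 1.76 |
| 50% | 2.32 | 1.5 | 2.0 | 2.05 |

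At each s, the last column is below the second. Restricting the group costs precision but still gives a tighter statement about in-utero exposure than the diluted group does.

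**Reserve in the sample size.** Table 4 gives 200 + 700 + 200 + 400 = 1500 first-trimester pregabalin pregnancies. At N=1500 and 119:1 the limit is 1.511. The diluted equivalent, 1 + 0.511/(1 − s), stays at or below 1.658 while 1 − s ≥ 0.511/0.658 = 0.78, so up to s of about 22%. This holds only if Table 4 was counted over the protocol window, which is not stated. There is some reason for doubt. Section 6 says that 21% of Danish first-trimester exposed pregnancies had an identifiable indication, and Table 1 counts 74 of them, which implies 74/0.21 ≈ 350. Table 4 shows 200 for first trimester and 350 for any time.

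**Active comparators.** Both groups can be diluted. Suppose each drug has a ratio of 1.3 against unexposed, with 10% of the pregabalin group and 50% of the comparator group not exposed in utero. The true ratio of 1.00 is then observed as (1 + 0.9 × 0.3)/(1 + 0.5 × 0.3) = 1.27/1.15 = 1.10. With 40% and 10% instead, it is 1.18/1.27 = 0.93. The direction is not fixed.

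**The case against.** Several points on the other side stand.

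- A reader might infer that every ratio is pulled towards 1. The protocol does not support that. Of the 16 contrasts in section 8.7.3.1, 12 use active comparators with the same window, and these can move either way. Residual confounding can also reverse the shift against unexposed: with confounding of 1.3, a true ratio of 0.8 and s = 20%, the ratio moves from 1.3 × 0.8 = 1.04 to 1.3 × 0.84 = 1.09. If the true ratio is 1, dilution changes nothing.
- A reader might take s = 31% from section 8.4, where agreement between dispensings and antenatal "records included in the birth register was 69% for antiepileptics in Sweden". That figure covers antiepileptics in general and not the pre-LMP window, and it does not show which source is wrong. It is not an estimate of s.
- A pack dispensed before LMP may still be in use afterwards, and a woman who stops on learning of the pregnancy has been exposed. So s is smaller than the share with pre-LMP dispensings only.
- The look-back is deliberate: section 8.2 plans for three months of preconception dispensing data. It gives no reason for counting those months as exposure.
- Table 4 is openly a count of dispensings, and 1.66 is not miscalculated.
- A SAP or Annex 3, whose contents are not shown, could add detail. But the exposure rule and the list of sensitivity analyses are already fixed in the protocol, and the general caveat in section 8.9 neither tests the rule nor limits its effect.

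**Conclusion.** The point holds in a limited form. The exposure rule does not match the stated in-utero objective, it can place unexposed pregnancies in the exposed group for every outcome, and nothing planned shows how much that matters. For the comparison with unexposed, dilution of a true excess risk is the expected result, provided confounding is controlled. For lamotrigine and duloxetine no direction can be stated.

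The 1.66 limit is right for dispensing-defined exposure at N=1000. Read as a limit for in-utero exposure, it would be about 1.73 to 2.32 over the assumed range of s. If Table 4's 1500 was counted over the same window, the reserve covers s up to about 22%. The true s is unknown, so these figures show sensitivity and do not estimate bias. A change is advisable; the broad definition itself need not be abandoned.

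**What to change.** 1. Keep LMP-90 as the broad definition.
2. Add to section 8.7.6 a pre-specified sensitivity analysis of the malformation and birth-outcome contrasts, at least those against unexposed. Require at least one dispensing on or after LMP within the relevant window: to LMP+97 for malformations, to the end of pregnancy for the others. Where active-comparator contrasts are included, apply the same rule to lamotrigine and duloxetine.
3. In that analysis, take pregnancies with pre-LMP pregabalin dispensings only out of the exposed group. Do not move them to the unexposed group. Report them separately as past users where numbers allow.
4. State in section 8.5 that the 1.66 limit refers to dispensing-defined exposure including the 90 days before LMP, and say which window the Table 4 counts used.
5. Align the Abstract's exposure wording with section 8.3.1.

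The dispensing dates are already extracted, but the work is more than one extra flag. Section 8.7.3.1 requires a separate propensity score for each population and contrast in each country. That means 4 sets per country (16 in all) for the contrasts against unexposed, including monotherapy, or up to 16 per country (64 in all) if every contrast is repeated, with trimming and balance checks each time. The restricted analysis has fewer exposed pregnancies and wider intervals. It also drops some women whose pre-LMP pack lasted into pregnancy, which costs precision but does not contaminate the unexposed group.

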3. ABSTRACT

Protocol A0081359 Version 1.0 23 November 2018

Title: A Population-based Cohort Study of Pregabalin to Characterize Pregnancy Outcomes

Rationale and background: Pregabalin (Lyrica[®], Pfizer Limited) was approved in July 2004 by the European Medicines Agency (EMA) for the treatment of peripheral neuropathic pain and as an adjunctive therapy for adult patients with partial onset seizures. Subsequently the marketing authorizations were expanded to include the additional indications of generalized anxiety disorder (GAD) in March 2006 and central neuropathic pain in September 2006.

A recent study using data from eight European Teratology Information Services (TIS), based on 164 pregabalin-exposed and 656 pregabalin-unexposed pregnancies, reported an increased risk in non-chromosomal major birth defects associated with first-trimester pregabalin exposure. A subsequent study based on 477 pregabalin-exposed pregnancies among Medicaid beneficiaries in the United States (US) did not confirm the increased risk. Pfizer is therefore conducting this study to address this issue.

This non-interventional study is designated as a Post-Authorisation Safety Study (PASS) and is a commitment to the EMA.

Research question and objectives:

The study objectives are to describe the use of pregabalin exposure in pregnancy and to estimate the risk of major congenital malformations, birth outcomes other than congenital malformations and neurodevelopmental outcomes with the use of pregabalin.

The primary objectives of the study are to:

- Describe use of pregabalin, lamotrigine, and duloxetine during pregnancy by
 - overall (as used in women for any therapeutic use),
 - trimester,
 - indication,
 - cumulative dose
 - calendar year of delivery,
 - as both overall and in the subcategory of monotherapy (no concomitant administration with other antiepileptic drugs AEDs);
- Describe the prevalence of major congenital malformations after first-trimester in-utero exposure to pregabalin (yes/no); after first-trimester exposure to lamotrigine, after first-trimester exposure to duloxetine and after first-trimester exposure to lamotrigine or duloxetine;
- Estimate the association between first-trimester exposure to pregabalin and prevalence of major congenital malformations, as compared with no exposure to

- pregabalin; exposure to lamotrigine; exposure to duloxetine; and exposure to lamotrigine or duloxetine;

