8.7.3.1. Computation of propensity scores

To account for confounding by the measured covariates, adjusted analysis will be conducted using propensity score (PS) stratification, following the approach by Paterno et al.⁴ For each pregnancy, a PS will be computed, using logistic regression, as the probability being exposed to pregabalin vs. given comparator conditional on the measured covariates listed in [Section 8.3.3](#) and [Annex 3](#).⁵³

PS will be estimated for each pregnancy using a generic-outcome model, meaning that all prespecified covariates will be included in the PS-estimating model, regardless of the outcome. Wyss et al showed, in a simulation study, that such model performs well when multiple outcomes are being examined;⁵⁴ furthermore, it is reasonable to assume in this study that all confounders distort the association in the same direction for all outcomes. In case of model non-convergence, covariates with the smallest cell counts (corresponding to the lowest prevalence of covariates) will be removed one-by-one until convergence is achieved.

A separate PS will be estimated for each study population and contrast. To summarise, the following sets of propensity scores will be estimated:

1. First-trimester pregabalin vs. first-trimester unexposed
2. First-trimester pregabalin vs. first-trimester lamotrigine
3. First-trimester pregabalin vs. first-trimester duloxetine
4. First-trimester pregabalin vs. first-trimester duloxetine or lamotrigine
5. First trimester pregabalin monotherapy vs. first-trimester unexposed
6. First trimester pregabalin monotherapy vs. first-trimester lamotrigine monotherapy
7. First trimester pregabalin monotherapy vs. first-trimester duloxetine monotherapy
8. First-trimester pregabalin monotherapy vs. first-trimester duloxetine or lamotrigine monotherapy
9. Any-trimester pregabalin vs. any-trimester unexposed
10. Any-trimester pregabalin vs. any-trimester lamotrigine
11. Any-trimester pregabalin vs. any-trimester duloxetine
12. Any-trimester pregabalin vs. any-trimester duloxetine or lamotrigine
13. Any-trimester pregabalin monotherapy vs. unexposed
14. Any-trimester pregabalin monotherapy vs. any-trimester lamotrigine monotherapy
15. Any-trimester pregabalin monotherapy vs. any-trimester duloxetine monotherapy
16. Any-trimester pregabalin monotherapy vs. any-trimester duloxetine or lamotrigine monotherapy

After estimation of each PS, the following steps will be taken in each country:

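### Pregabalin monotherapy does not exclude duloxetine although the unexposed group must, and the combined lamotrigine-or-duloxetine comparator has no co-exposure rule

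*Protocol*

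**What the plan says.** Section 8.3.1 defines first-trimester pregabalin monotherapy by the absence of other AEDs: "Pregabalin monotherapy in the first trimester will be defined as first-trimester exposure to pregabalin and no first-trimester dispensing for any other AED". The any-time version is the same: "any-pregnancy exposure to pregabalin and no dispensing for any other AED during any trimester". The abstract agrees: "monotherapy (no concomitant administration with other antiepileptic drugs AEDs".

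The first-trimester unexposed comparator is "pregnancies without a dispensing for pregabalin or any other AED, including lamotrigine or duloxetine, during the first trimester". Duloxetine monotherapy is "first-trimester exposure to duloxetine and no first-trimester dispensing for any AED".

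Co-exposed pregnancies are removed when lamotrigine alone is the comparator and when duloxetine alone is. The duloxetine rule reads: "For analyses that use duloxetine as the comparator, pregnancies exposed to both pregabalin and duloxetine in the first trimester will be excluded". Both rules are repeated for exposure at any time in pregnancy. Neither window has such a rule for the third active comparator, lamotrigine or duloxetine, although it has its own propensity-score models (contrasts 4, 8, 12 and 16 in Section 8.7.3.1).

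A sensitivity analysis tightens monotherapy, which "will be defined by absence of other AED, selective serotonin reuptake inhibitors, or benzodiazepines". Duloxetine is not on that list, and Section 8.7.6 plans crude estimates only for this analysis.

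**The concern.** Contrast 5, "First trimester pregabalin monotherapy vs. first-trimester unexposed", and its any-trimester counterpart, contrast 13, are where a reader will look for an association with pregabalin free of other study drugs. As defined, the exposed arm may include duloxetine users and the reference arm may not, so the estimate describes pregabalin with or without duloxetine. Co-use is plausible because the protocol chose duloxetine for sharing the neuropathic pain and GAD indications.

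Two features of the plan make this matter:

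- Section 6 cites pooled risk ratios of 1.3 for any first-trimester pregabalin exposure and 1.0 for monotherapy, so the monotherapy estimate will carry weight in interpretation.
- Section 8.1 proposes to judge confounding from how estimates change with the comparator. Contrast 7 drops pregabalin-plus-duloxetine pregnancies while contrasts 5 and 6 can keep them, so the exposed group changes along with the comparator.

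For the combined comparator, the definitions do not say in which arm a co-exposed pregnancy belongs. Analyses run separately in each country (Section 8.7), so four analysts could settle this differently, and the coordinating centre would see only aggregate estimates.

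**Working it through.** **Step 1: is duloxetine an AED in this protocol?** The pregabalin and lamotrigine monotherapy definitions bar any *other* AED. The duloxetine definition bars any AED, without *other*, which makes sense only if duloxetine is not one. The abstract's unexposed definition lists duloxetine as a condition separate from the AEDs, and the any-trimester unexposed definition in 8.3.1 sets it apart by a comma. Against this, the first-trimester unexposed definition ("pregnancies without a dispensing for pregabalin or any other AED, including lamotrigine or duloxetine, during the first trimester") can be read as counting duloxetine among the AEDs. Most of the wording treats it as a non-AED, but the text is not consistent.

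**Step 2: apply the definitions, with duloxetine as a non-AED, to the 16 contrasts in Section 8.7.3.1.**

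| Contrasts | Result |
|---|---|
| 1, 9 | All pregabalin users v unexposed; co-medication in the exposed arm is open and intended |
| 2, 10 | Pregabalin-lamotrigine overlap excluded |
| 3, 11 | Pregabalin-duloxetine overlap excluded |
| 4, 12 | No rule; pregabalin plus lamotrigine or duloxetine meets both arm definitions |
| 5, 13 | Duloxetine possible in the exposed arm, barred from the reference arm |
| 6, 14 | Duloxetine possible in both arms |
| 7, 15 | Pregabalin-duloxetine overlap excluded |
| 8, 16 | Comparator bars pregabalin as another AED, so no dual membership; pregabalin plus duloxetine can stay in the pregabalin arm |

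**Step 3: can the propensity score repair contrasts 5 and 13?** Section 8.3.3 enters antidepressants as one yes/no class. No unexposed pregnancy can have duloxetine, so duloxetine itself cannot be balanced. Women taking it would be matched at best to users of other antidepressants.

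**Step 4: possible size in contrasts 5 and 13.** The co-exposed share f and the duloxetine risk ratio r are assumptions, since the protocol gives neither. With no pregabalin effect and before adjustment, the expected ratio is 1 + f(r − 1):

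- f = 5%, r = 1.2: 1 + 0.05 × 0.2 = 1.01
- f = 5%, r = 1.5: 1 + 0.05 × 0.5 = 1.025
- f = 10%, r = 1.2: 1 + 0.10 × 0.2 = 1.02
- f = 10%, r = 1.5: 1 + 0.10 × 0.5 = 1.05

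For scale, Table 4 sums to 200 + 700 + 200 + 400 = 1,500 first-trimester pregabalin pregnancies, so 5-10% is 75-150. That base is all pregabalin users. The monotherapy subset is smaller and its size is not stated.

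**Step 5: possible size in contrast 4.** Table 4 gives 6,200 lamotrigine and 1,800 duloxetine first-trimester pregnancies, at most 8,000 together. If 75-150 overlapping pregnancies were counted in the comparator arm as well, their share c would be 75/8,000 = 0.9% to 150/8,000 = 1.9%. A true pregabalin ratio of 1.5 would read 1.5/(1 + 0.5c), that is 1.493 to 1.486.

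**Step 6: precision cost of removing co-users.** Section 8.5 states an upper limit of 1.65845 for 3% prevalence, 1,000 exposed and a 119:1 ratio. With SE = √[0.97/(1,000 × 0.03) + 0.97/(119,000 × 0.03)] = 0.1806, exp[(1.960 + 0.842) × 0.1806] = 1.658, which reproduces it. Keeping 119,000 in the reference group, 950 exposed gives 1.680 and 900 exposed gives 1.704.

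**The case against.** The strongest reply is that monotherapy here means AED monotherapy, a stated choice made the same way in the abstract and in both exposure windows. Section 7 calls the monotherapy assessment a sensitivity analysis, and a reference group free of all study drugs is a deliberate background comparator that contrasts 1 and 9 share. That answers any charge of oversight. It does not remove the asymmetry in contrasts 5 and 13, and the abstract lists the monotherapy analyses among the primary ones.

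A second reply is that the first-trimester unexposed wording makes duloxetine an AED and so closes the gap. The duloxetine monotherapy definition and the abstract contradict that reading. Even if it were adopted, it would not supply the missing rule for contrasts 4 and 12.

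A third is that the two single-drug exclusions extend naturally to a comparator built from those drugs. This is reasonable as intent, but it is not written. Operational detail may also sit in Annex 3, whose content is not shown.

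A reader might also infer a large bias. A factor of 1.15, for instance, needs 15% co-use and a duloxetine risk ratio of 2.0. The documents do not support that. Section 6 says the sparse duloxetine data do not point to a clinically important increase in risk. If the higher ratio is meant to capture disease severity, that part is confounding, which the propensity score addresses at least partly through depression, analgesics, hypnotics and health care use.

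**Conclusion.** The point holds as a defect of definition. On the wording most of the protocol uses, contrasts 5 and 13 can have duloxetine in the exposed arm only. The restricted monotherapy definition does not close that gap, and a class-level antidepressant covariate cannot balance duloxetine itself. Contrasts 4 and 12 lack an assignment or exclusion rule for co-exposed pregnancies. Contrasts 8 and 16 can keep pregabalin plus duloxetine in the pregabalin arm. The duloxetine-only contrasts (3, 7, 11, 15) and the pregabalin-lamotrigine overlap in 2 and 10 are already protected.

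The likely effect is small: about 1.01-1.05 before adjustment in contrasts 5 and 13, resting wholly on the assumed 5-10% co-use and risk ratio of 1.2-1.5. Two stronger inferences should be resisted. The protocol does not show that the monotherapy arm *does* contain duloxetine users, only that it can. Nor does the combined contrast become largely a comparison of a drug with itself: under the same co-use assumption, a true ratio of 1.5 moves only to about 1.49.

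**What to change.** In Section 8.3.1, for both exposure windows and for both the main and the SSRI/benzodiazepine-restricted versions:

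- Define pregabalin monotherapy **and** lamotrigine monotherapy as no other AED and no duloxetine. Changing pregabalin alone would leave duloxetine possible only in the lamotrigine arm of contrasts 6 and 14.
- Exclude pregnancies exposed to pregabalin plus lamotrigine, or pregabalin plus duloxetine, from the combined-comparator contrasts (4, 8, 12, 16).
- Reconcile the first-trimester unexposed wording with the abstract and the duloxetine monotherapy definition, so that duloxetine is plainly either an AED or not.
- Report the number co-exposed by country, which would settle the size of the issue.

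The cost is protocol wording and one further condition on dispensing data that the study already uses. The monotherapy groups shrink by the co-users. On the Section 8.5 scenario, losing 5-10% of exposed pregnancies moves the upper limit from 1.658 to 1.680-1.704.
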